H_1 = PRO-231 ophthalmic solution does not have a similar safety and tolerability profile as VIGAMOXI® in clinically healthy subjects.

$$H_1: ST_A \neq ST_B \text{ o } ST_A - ST_B \neq 0$$

Operational definition of similarity: To reject H_0 , the p-value in the primary variables must be ≤ 0.05 and the 95% CI of this difference must not include zero. Both conditions for hypothesis testing (p-value and 95% CI) must be met, otherwise the result will be interpreted as "**absence of evidence**", not "**evidence of absence**".

Study Design: Phase I clinical study, controlled, comparative, parallel-group, single-blind, single-center.
Number of subjects (planned and analyzed): Number of planned subjects: 38 (19 subjects per arm).
Diagnosis and main inclusion criteria: Ophthalmologically and clinically healthy subjects.
Selection criteria: Inclusion criteria: 
– Have the ability to voluntarily give their signed informed consent.– Ophthalmologically and clinically healthy subjects.– Be able and willing to comply with scheduled visits, treatment plan, and other study procedures.– Age 18 to 45 years.– Both sexes.– Women of childbearing potential must ensure the continuation (initiated \geq 30 days prior to signing the informed consent form [ICF]) of the use of a hormonal contraceptive method or intrauterine device (IUD) during the study period.– AVMC of 20/30 or better in both eyes.– Corneal staining \leq grade I on the Oxford Scale.– Have an intraocular pressure \geq 10 and \leq 21 mmHg. Exclusion criteria: 
– History of hypersensitivity to fluoroquinolones or any of the components of the PI.– Be a user of topical ophthalmic medications of any pharmacological group.– Be a user of medicines by any other means of administration.– History of eye surgery in the last 6 months.– Wearing contact lenses for less than two weeks prior to the start of the study, and during the study intervention period.– For women: being pregnant, breastfeeding, or planning to become pregnant within the study period.– Have participated in any investigational clinical study 30 days prior to inclusion in this study.– Have previously participated in this same study.– History of any chronic-degenerative disease, including Diabetes Mellitus or Systemic Arterial Hypertension.– Known diagnosis of liver or heart disease.– Have active inflammatory or infectious disease at the time of study entry.

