- Incidence of conjunctival hyperemia and chemosis. (TE: day 3 and 8)
- Changes in the AVMC evaluated with the Snellen chart. (TE: day 3 and 8)
- Changes in ocular surface integrity using fluorescein staining, using the Oxford scale. (TE: day 3 and 8).

Tolerability

- ICO score changes. (TEE: day 8)

Secondary outcome variables:***Safety:***

- Incidence of expected and intervention-related AEs (excluding conjunctival hyperemia and/or chemosis). (TE: day 3, 8 and 12)

[figure not shown]
Tolerability:

- Presence of eye symptoms (burning, foreign body sensation, pruritus and tearing). (TE: day 3 and 8)

Statistical methodology

The analysis of the data collected in the study will be carried out by means of specialized statistical software (SPSS available version or R software). The data will be expressed with measures of central tendency: mean, standard deviation and/or ranges for quantitative variables, and frequencies and/or percentages for qualitative variables. The Shapiro-Wilk test (S-W) will be used to determine if the distribution is normal in the data obtained in each study group ($p>0.05$). If the normality in the distribution of the data is verified, to rule out differences between groups, the Student's t-statistic will be used for independent groups, while intragroup differences will be analyzed with the Student's t-test for repeated measures. In case of $p<0.05$ in S-W, the statistical analysis to rule out differences between groups will be performed by means of the Mann-Whitney U test for quantitative variables, while intragroup differences will be performed by Wilcoxon's rank test. The difference between the qualitative variables will be analyzed by means of the χ^2 statistic (Chi-squared) or Fisher's exact (for expected values less than 5). Dichotomous variables will be analyzed by the McNemar test when applicable. An alpha (α) ≤ 0.05 will be considered as statistical significance, in addition to this, the 95% CI will be calculated for these differences. For primary outcome variables, H_0 will be rejected, when $p \leq 0.05$ and the 95% CI does not include zero.

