2.3 Problem statement

Bacterial conjunctivitis is one of the most common eye infections and it is estimated that it represents up to 1% of consultations at the first level of care, generating a significant economic and social impact, as a result of the interruption of the patient's normal activities, as well as absenteeism from work and/or school. Although it is usually a self-limiting condition, with an average duration of 1 to 2 weeks, empirical treatment with broad-spectrum anti-infective drugs is recommended to shorten the course of the disease, improve patient comfort, decrease transmissibility, promote early return to work or school, and reduce the risk of serious complications that may compromise vision [9][1, 2, 3, 4, 5, 6, 7]

Fluoroquinolones are antibiotics whose usefulness in the area of ophthalmology has already been proven, as they have been used for decades as a treatment and/or prophylaxis for eye infections. Its effectiveness and safety have given this family of drugs a significant place within the therapeutic options of today's ophthalmologist; however, despite being generally well-tolerated drugs with low toxicity, it was decided to compare PRO-231 with VIGAMOXI,® the topical formulation of moxifloxacin 0.5% currently marketed in our country, to verify that its safety and toxicity profile is equal to the latter.

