2.4 Rationale for the study

Although eye infections can be considered minor infections, in some cases, they can become complicated and leave irreversible sequelae that can compromise the patient's vision. For this reason it is important to prescribe topical antibiotics for the treatment of eye infections, or as prophylaxis in surgical procedures and eye trauma. An important property of anti-infective drugs is their selective

toxicity, eliminating microorganisms while causing minimal or no adverse reactions to the host. [17, 18] [1]

Moxifloxacin hydrochloride, the active ingredient in PRO-231 ophthalmic solution, is a fourth-generation fluoroquinolone, which has already been approved for use in the treatment of bacterial conjunctivitis and keratitis caused by susceptible strains; and it is already marketed by international ophthalmic product laboratories. It has the advantage of being preservative-free, and in addition, offers broad-spectrum activity, and a moderate to high clinical success rate against common ocular pathogens. In addition to this, thanks to its concentration and its high penetrance to the ocular tissues, it allows a dosing regimen at infrequent intervals, simplifying its administration and making it more convenient for patients. [6, 7, 9, 10]

In our country, this antibiotic formulation is marketed and approved under the name VIGAMOXI® (Alcon Laboratories, Inc. Fort Worth, Texas, USA) for the treatment of bacterial conjunctivitis. Clinical studies are required to evaluate that the safety and tolerability of PRO-231, prepared by Laboratorios Sophia S.A. de C.V., is comparable to that of VIGAMOXI,® and which are the basis of future clinical studies that prove its efficacy. The current commitment of Laboratorios Sophia, S.A. de C.V. is to generate its own information for its products that serves for the pertinent regulatory procedures, and as a scientific basis for their commercialization.

3. Objectives and hypotheses

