3.2 Study hypothesis

H0: PRO-231 ophthalmic solution has a similar safety and tolerability profile as VIGAMOXI® in clinically healthy subjects.

$$H_0: ST_A = ST_B \text{ o } ST_A - ST_B = 0$$

H1: PRO-231 ophthalmic solution does not have a similar safety and tolerability profile as VIGAMOXI® in clinically healthy subjects.

$$H_1: ST_A \neq ST_B \text{ o } ST_A - ST_B \neq 0$$

Operational definition of similarity: To reject H0, the p-value in the primary variables must be ≤ 0.05 and the 95% CI of this difference must not include zero. Both conditions for hypothesis testing (p-value and 95% CI) must be met, otherwise the result will be interpreted as "**absence of evidence**", not as "**evidence of absence**".

4. Study design

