10.1.1 Calculation methodology

Although sample estimation in phase 1 studies is common in treatments whose toxicity/risk is high, as it is in clinical studies for the management/survival of cancer; It was considered pertinent to estimate the sample size according to the safety profile reported in the literature after the use of moxifloxacin hydrochloride. Considering the primary safety variables of the protocol: [59]

- Incidence of AD
- Changes in ophthalmologic signs
- Changes in the AVMC
- Changes in fluorescein staining of the ocular surface

The equation was used to compare two proportions: two samples, two sides of equality. This calculation is useful when you want to test whether the proportions of two groups are different (Incidence of AD in VIGAMOXI® is different from the incidence of AD in PRO-231). The following formulas are used for the calculation to compute the sample size and power respectively: [60]

$$n_A = kn_B \text{ y } n_B = \left(\frac{p_A(1 - p_A)}{k} \right) \left(\frac{z_{1-\alpha/2} + z_{1-\beta}}{p_A - p_B} \right)^2$$

$$1 - \beta = \Phi\left(z - z_{1-\alpha/2}\right) + \Phi\left(-z - z_{1-\alpha/2}\right), z = \frac{p_A - p_B}{\sqrt{\frac{p_A(1-p_A)}{n_A} + \frac{p_B(1-p_B)}{n_B}}}$$

Where:

$k = n_A/n_B$: ratio between the sample sizes of the two groups

Φ : Function of Standard Normal Distribution

Φ^{-1} : The standard normal quantile function

α : error tipo I

β : error tipo II

The proportion of subjects who had at least one AE (ocular and non-ocular) was considered in the study by Garg et al. (2015), where they evaluated the clinical and antibacterial efficacy, as well as the safety of besifloxacin ophthalmic suspension compared to moxifloxacin 0.5% (besifloxacin; n=61, moxifloxacin; n=62). A total of 6 ocular AEs were present in subjects treated with moxifloxacin and at least one AE occurred in 3 patients. The most common AE was conjunctivitis (3.2%). For the expected proportion of subjects of PRO-231, 50% was used, which is a conservative value and gives larger samples. The calculation was made using the free software R (R Core Team, 2021), using a code available online for this purpose. [56] [61] [62]

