10.3.1 Population Analysis

The statistical analysis will be presented to give a general summary of the subjects entered into the study and a view of the safety and tolerability of its results. The data provided by the research site will be summarized for this purpose, according to its nature. The Shapiro-Wilk test will be performed to find out if the quantitative data are distributed in a normal way ($p>0.05$).

The results of the quantitative variables will be presented in measures of central tendency: mean, standard deviation and/or ranges. Changes in the AVMC and ICO will be expressed as continuous variables. Whereas, the incidence (number) of AEs will be expressed as a discrete variable.

The result of the nominal and ordinal qualitative variables will be presented in frequencies, proportions and/or percentages. For these, tables of frequencies $p \times q$ will be constructed. All percentages will be presented with a decimal.

The level of difference to consider significance will be an alpha (α) of 0.05 or less, the 95% CI will be calculated for these differences. The triangulation between the type of variable and the measurements is shown in Table 5. [63]

The operational definition of the study for hypothesis testing will be as follows:

Hypothesis testing	value	Result	Interpretation
P value	≤ 0.05		
95% CI	Does not include zero	H_0 rejected	Both treatments are different in terms of safety and tolerability
P value	≥ 0.05	H_0 accepted	Both treatments are similar in terms of safety and tolerability (they are not different)
95% CI	Includes zero		

Both conditions for hypothesis testing (p-value and 95% CI) must be met, otherwise the result will be interpreted as "**absence of evidence**", not as "**evidence of absence**".

Board 5. Triangulation of concepts.

Variable Type	Variable	A1	A2	B1	C1	C2	C3	C4	D1	E1	F1	F2	F3	F4
Selection														
A1	Demographic			D										
A2	Medical History/Selection Criteria				D									
Basal														
B1	Comprehensive ophthalmological evaluation			T	D	TB	TB	B	T		TB			
Primary Security														
C1	Incidence of unexpected-related AEs				TB					TB				
C2	Incidence of conjunctival hyperemia and chemosis			T		TB				TB				
C3	AVMC			B	TB			B		TB				
C4	Corneal and conjunctival stains with fluorescein			B	TB			B		TB				
Primary Tolerability														
D1	ICO								B					
Secondary Security														
E1	Incidence of AE*			T			TB							
Secondary Tolerability														

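### The decision table in 10.3.1 turns a non-significant test of equality into a finding of similarity, with no margin and against 1.1 and 3.2

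*Combined protocol and SAP*

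**What the plan says.** The synopsis (1.1) and section 3.2 set H0 as a difference of exactly zero between the products and H1 as any non-zero difference. The rule in 3.2 reads "To reject H0, the p-value in the primary variables must be ≤ 0.05 and the 95% CI of this difference must not include zero". The sentence that follows, "Both conditions for hypothesis testing (p-value and 95% CI) must be met, otherwise the result will be interpreted as", sends everything else to absence of evidence and expressly not to evidence of absence. The statistical paragraph of the synopsis also contains only a rejection rule ("For primary outcome variables, H_0 will be rejected, when" both conditions are met).

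Section 10.3.1 adds a two-row table. Row one rejects H0. Row two takes p ≥ 0.05 with a CI that includes zero, marks H0 as accepted, and gives the interpretation "Both treatments are similar in terms of safety and tolerability (they are not different". The same both-conditions sentence is repeated under the table.

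The aims in the background are worded as sameness: section 2.3 wants "to verify that its safety and toxicity profile is equal to the latter", and section 2.4 wants evidence that the safety and tolerability of PRO-231 "is comparable to that of VIGAMOXI". No equivalence or non-inferiority margin appears anywhere.

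**The concern.** A test of equality can give evidence against equality. When it fails to do so, the products may be alike or the data may be too few to tell, and the p-value does not separate the two. A CI that includes zero can also include a large excess of harm. Calling that result similarity requires a margin that the CI must lie within, and the plan has none.

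The row governs every primary variable and is the plan's only formal route to the sameness claims in 2.3 and 2.4. Under it, less precise data make the favourable conclusion more likely. The plan also leaves two instructions for the most likely result, inconclusive in 1.1 and 3.2 and similar in 10.3.1, so the choice could be made after the results are known.

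**Working it through.** **1. What the sample size was built for.** Section 10.1.1 uses a two-sided comparison of two proportions, with 50% for PRO-231 and a control rate from a cited patient study with 62 moxifloxacin subjects ("A total of 6 ocular AEs were present in subjects treated with moxifloxacin and at least one AE occurred in 3 patients"). Power is not stated; I assume 80%. With both variance terms and 6/62 = 9.7%:

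n = [0.0968 × 0.9032 + 0.50 × 0.50] × [(1.960 + 0.842)/(0.50 − 0.0968)]² = 16.29, rounded up to 17; 17 × 1.1 = 18.7, rounded up to 19.

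This reproduces the plan's 17 and 19 per arm (3/62 = 4.8% gives 12). The design therefore looks for a gap of about 40 percentage points. Nothing in it bounds a smaller gap.

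**2. The texts side by side**, for p ≥ 0.05 with a CI that includes zero:

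| Place | Conditions listed | Reading of this result |
|---|---|---|
| 1.1 and 3.2, hypothesis | the two for rejection | inconclusive |
| 1.1, statistics | the two for rejection | none beyond not rejecting |
| 10.3.1, table row 2 | p ≥ 0.05, CI includes zero | H0 accepted, similar |

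The sentence under the table does not cancel row 2, because this result meets both conditions of that row. There it catches only cases where p and CI disagree. In addition, p = 0.05 exactly satisfies the p condition of both rows.

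**3. Observed results that fall in row 2 at 17 per arm.** No event rate has to be assumed. The test follows the plan: Fisher if an expected count is below 5, otherwise chi-square. The plan names no CI method for proportions; I use Newcombe's.

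Example, 5/17 vs 1/17. The Wilson limits are 13.3% to 53.1% and 1.0% to 27.0%, and the difference is 0.235.
- Lower limit: 0.235 − √[(0.294 − 0.133)² + (0.270 − 0.059)²] = −0.030.
- Upper limit: 0.235 + √[(0.531 − 0.294)² + (0.059 − 0.010)²] = 0.477.

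| Result | p | 95% CI, points |
|---|---|---|
| 3/17 vs 0/17 | 0.23 (Fisher) | −4 to +41 |
| 5/17 vs 1/17 | 0.17 (Fisher) | −3 to +48 |
| 8/17 vs 3/17 | 0.067 (chi-square) | −2 to +54 |
| 0/17 vs 0/17 | 1.00 (Fisher) | −18 to +18 |

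**4. Probability of row 2 for one binary variable.** I summed exact binomial probabilities over all outcomes with p ≥ 0.05 and a CI that includes zero. The ranges run from the Wald to the Newcombe interval. The documents give no expected rates for the primary variables, so the control rates are assumptions. The 4.8% is 3/62 subjects; the 9.7% is 6/62, an event count used only as an upper illustration.

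| True rates | 17 per arm | 19 per arm |
|---|---|---|
| 4.8% vs 10% | 96% | 95% |
| 4.8% vs 15% | 88% | 85% |
| 9.7% vs 20% | 87–88% | 85–86% |
| 9.7% vs 30% | 66–69% | 61–65% |
| 20% vs 40% | 73–77% | 69–72% |
| 15% vs 45% | 47–52% | 41–45% |
| 20% vs 60% | 29–30% | 22% |
| 4.8% or 9.7% vs 50% (planning rate) | 8–24% | 5–18% |

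**5. Continuous variables (t-test, 17 per arm).** The critical value is t(0.975, 32) = 2.037 and the noncentrality is δ√(17/2), with δ in SD units because no SD is given. Row 2 is reached with probability 1 − power: 86% for δ = 0.3, 71% for δ = 0.5, 38% for δ = 0.8. The CI half-width is 2.037 × √(2/17) = 0.70 SD.

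**The case against.** The best defence is that the both-conditions sentence is essentially the same in 1.1, 3.2 and 10.3.1 and can be read the same way throughout: p and CI must agree, and only disagreement is inconclusive. The heading in 3.2 ("Operational definition of similarity: To reject H0, the p-value in the primary variables must be" …) suggests that some result is meant to count as similar. On that reading the sections do not contradict one another. But 1.1 and 3.2 list only the conditions for rejection, so the literal reading there is the one above. The uniform reading also removes only the contradiction: row 2 would still treat non-rejection as similarity.

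The illustrations have limits, and these stand. Hyperemia is graded 0 to IV, and the plan states no cut for its incidence, so treating it as binary is a simplification. Unexpected related AEs are also listed as a count. The assumed rates come from any AE in treated patients, not healthy volunteers. The observed results in step 3 do not depend on those rates.

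It is also fair that this is a 38-subject phase I study, that no data collection changes, and that planned CIs would make the imprecision visible. That is a reason not to ask for more subjects. It does not excuse a rule that tells the analyst to report an imprecise result as similarity.

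**Conclusion.** The point holds and should be corrected before the data are unblinded. Row 2 is invalid as written: H0 is exact equality, the tests look for a difference, and there is no margin. On the literal reading it also contradicts 1.1 and 3.2. Neither conclusion depends on an assumed rate.

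The size does depend on assumptions. For control rates of about 10% or less, a doubled or tripled binary rate would usually be reported as similar. For a tripled rate the chance is close to even at 15% control (41–52% across 17 and 19 per arm) and 22–30% at 20%. All probabilities are per variable, not for the overall conclusion. The binary figures illustrate hyperemia, chemosis and subjects with an unexpected related AE; the t-test figures illustrate AVMC and ICO if normality holds. Neither set covers the ordinal Oxford grade.

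**What to change.** - Delete the second row of the table in 10.3.1, which also removes the overlap at p = 0.05.
- State identically in 1.1, 3.2 and 10.3.1 that any result not meeting both rejection conditions is reported as: no difference was demonstrated (inconclusive).
- Retitle the rule in 1.1 and 3.2 as the rule for rejecting equality, since it does not define similarity.
- For each primary variable, report the planned 95% CI and the largest difference it does not exclude. Name the method for proportions (Newcombe or Miettinen–Nurminen). For the Oxford grade, and wherever Mann–Whitney replaces the t-test, name the effect measure to which the CI refers.

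The cost is wording in three places, one heading, and the choice of CI methods; no subjects are added. The sponsor gives up concluding equal, similar or comparable from non-significance, so the aims in 2.3 and 2.4 should be read, or reworded, as estimation.

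Keeping a similarity claim would need a justified margin and an equivalence test. For scale only, with assumed margins m, equal true rates p, two one-sided 5% tests and 80% power, n = 2p(1 − p)[(1.645 + 1.282)/m]² per arm. Margins of 10, 15 and 20 points need 79, 36 and 20 per arm at p = 4.8%, and 150, 67 and 38 at p = 9.7%. That redesign is not requested here.

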7.4 Outcome variables

7.4.1 Primary outcome variables

7.4.1.1 Security

- Incidence of unexpected AEs related to interventions.
- Incidence of conjunctival hyperemia and chemosis.
- Changes in the AVMC evaluated with the Snellen chart.
- Changes in ocular surface integrity using fluorescein staining, using the Oxford scale.

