7.4.2 Secondary outcome variables

7.4.2.1 Security

- Incidence of expected and intervention-related AEs (excluding conjunctival hyperemia and/or chemosis).

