7.4.3 Definition of variables, methods and scales for their measurement

Board 2. Operational definition of variables

Variable	Conceptual Definition	Operational Definition	Measurement Type	Reference value	Statistical test
Incidence of Intervention-Related Unexpected AEs	Any adverse medical event that occurs in the clinical research subject to whom any of the interventions were administered and that has a certain coincidental relationship to the interventions [33]	All AEs (according to protocol) in which the PI suspects a causal relationship with the interventions will be reported	• Discrete quantitative • Nominal qualitative	• Relationship with IP • Severity • Causality	
 • Student's t-test of independent groups • U de Mann Whitney* • Pearson X² or Fisher Exact*
Incidence of conjunctival hyperemia	It is the reaction of the conjunctiva to a stimulus, a red appearance secondary to the vasodilation of the conjunctiva vessels of variable intensity is seen	Direct observation. Classification by Efron scale. See attachment 16.2. Efron Scale for Conjunctival Hyperemia	Degrees: 0 = Normal, I = Muy live, II = Mild, III = Moderate and IV = Severe		
 • Pearson X² or Fisher Exact* • McNemar Test*
Incidence of Chemosis	It is defined as conjunctival edema, the result of an inflammatory reaction. It is classified as present or absent	The evaluator will use a narrow beam of light at 60° and will measure whether the conjunctiva separates ≥ 1/3 of the total	• Nominal qualitative	Present / Absent	
 • Pearson X² or Fisher Exact* • McNemar Test*

Variable	Conceptual Definition	Operational Definition	Measurement Type	Reference value	Statistical test
Changes in the AVMC	Visual spatial acuity is the ability to distinguish separate elements of an object and identify them as a whole. It is quantified as the minimum angle of separation (located at the nodal point of the eye) between two objects that allows them to be perceived as separate objects	eyelid opening or if it exceeds the gray line Cartilla de Snellen. Ver anexo 16.5 Fraction to LogMAR conversion table.	• Continuous quantitative	20/30 (0.2 LogMAR) or better	
 • Student's t-test of independent groups • U de Mann Whitney*

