Changes in the integrity of the ocular surface	Detection of corneal and conjunctival epithelial defects by means of the CT using the Oxford scale	Direct observation with slit lamp, graduation on Oxford scale. See attachment 16.3 Oxford scale	• Ordinal qualitative	Degrees: The TF is presented in a series of panels (A – E). The staining points vary from 0 – 5 for each panel and from 0 – 15 for the total exposed area of the conjunctiva and cornea	
 • Pearson X2 or Fisher Exact* • McNemar Test*
ICO score changes	The ICO is a questionnaire designed to measure irritation of the ocular surface, it assesses symptoms focused on the comfort associated with ocular surface alterations. Elevated values indicate more severe symptoms	The evaluator will apply the questionnaire to the subject and allow the subject to answer it calmly without any pressure and/or coercion. See annex 16.4 Eye Comfort Index (JI)	• Continuous quantitative	0 – 100	
 • Student's t-test of independent groups • U de Mann Whitney*

Variable	Conceptual Definition	Operational Definition	Measurement Type	Reference value	Statistical test
Incidence of expected and intervention-related AEs (excluding conjunctival hyperemia and/or chemosis). (bis)	Any adverse medical event that occurs in the clinical research subject who was administered any of the interventions and that has a causal relationship to them [33]	All intervention-related AEs will be reported according to the protocol.	• Discrete quantitative • Nominal qualitative	• Incidence • Severity • Causality	
 Independent group student's t-test U de Mann Whitney* Pearson X² or Fisher Exact*
Incidence of eye symptoms (burning, SCE, pruritus, and tearing)	
Burning: refers to the sensation of stinging or eye irritation.
 
SCE: refers to the sensation of "sand" inside the eye.
 
Pruritus: This refers to the itching or tickling sensation caused by the need to rub or scratch.
 
Tearing: It refers to excessive tear production [34, 35, 36, 37]
	The evaluator will perform the interrogation to rule out or confirm the general presence of symptoms	• Nominal qualitative	Present / Absent	
 Pearson X² or Fisher Exact* McNemar Test*

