8.3 Use of adverse events as a study safety variable

Measuring the safety of the use of PRO-231 is paramount to the study, therefore, it is considered important to report any unwanted manifestations or diseases that occur during the course of the study, regardless of whether or not the manifestation is considered to be related to the treatment under investigation. [49]

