F1	Presence of burning								B	TB				
F2	ETS Presence								B		TB			
F3	Presence of pruritus								B		TB			
F4	Presence of tearing								B		TB			

Abbreviations: AVMC, best corrected visual acuity; B, bivariate analysis; D, descriptive statistics; AE, adverse event; ICO, eye comfort index; SCE, foreign body sensation; T, contingency table p x q. *EAs related or not, with the research product.

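### The secondary adverse event variable has two incompatible definitions: expected and related events only, or all events whatever their cause

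*Combined protocol and SAP*

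**What the plan says.** Section 7.4.2.1 defines the secondary safety variable as "Incidence of expected and intervention-related AEs (excluding conjunctival hyperemia and/or chemosis"). The synopsis and section 3.1.2.2 give the same definition. Table 2 (section 7.4.3) repeats it as the row title, and its operational definition reads "All intervention-related AEs will be reported according to the protocol".

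Table 5 (section 10.3.1) lists the secondary safety variable as row E1, "Incidence of AE", with an asterisk. The footnote to that asterisk reads "EAs related or not, with the research product". The asterisk is attached to no other row.

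The primary AE variable in section 7.4.1.1 is "Incidence of unexpected AEs related to interventions". Table 2 puts it into operation as "All AEs (according to protocol) in which the PI suspects a causal relationship with the interventions will be reported".

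Section 8.3, on the use of AEs as a safety variable, says unwanted manifestations should be reported "regardless of whether or not the manifestation is considered to be related to the treatment under investigation". Section 10.3.2.2 applies the primary tests to the secondary variables in all subjects who received at least one dose. It does not restate what the AE variable contains.

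**The concern.** The two definitions give opposite rules on relatedness. Row E1 also drops the restriction to expected events and the exclusion of hyperemia and chemosis, so the mismatch is wider than causality alone. It lies in current, intact text.

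In a trial whose main objective is safety and tolerability, the AE tables are central output. If the conflict stays open, the choice of definition could be made after the data are seen. If the narrower definition is followed, an event enters an AE comparison only after someone has judged it to be caused by the study product. Section 8.4 and section 8.5.4 describe several causality categories, but no section says which of them count as related.

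**Working it through.** The documents state no figure for this point. The check compares the definitions and then illustrates how sensitive the result is.

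**Step 1: the definitions side by side.**

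| Place | Expected only? | Related only? | Hyperemia and chemosis excluded? |
|---|---|---|---|
| Synopsis, 3.1.2.2, 7.4.2.1 | Yes | Yes | Yes |
| Table 2, row title | Yes | Yes | Yes |
| Table 2, operational definition | Not stated | Yes | Not stated |
| Table 5, row E1 and footnote | Not stated | No | Not stated |

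**Step 2: what the AE-incidence variables cover together.**

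- Primary: unexpected and related.
- Secondary under 7.4.2.1: expected and related, less hyperemia and chemosis.
- Union: related events only. An AE judged unrelated belongs to neither set.
- Secondary under Table 5: all AEs, so an unrelated AE is included.

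**Step 3: what is compared without a causality condition in any case.** Section 7.4.1.1 lists "Incidence of conjunctival hyperemia and chemosis", change in best-corrected visual acuity and change in Oxford staining as primary variables. Section 7.4.2.2 adds burning, foreign body sensation, pruritus and tearing. An unrelated event of one of these kinds is still compared through its own variable. The gap concerns all other AEs, including the non-ocular ones.

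**Step 4: how narrow the 7.4.2.1 variable could become.** Section 7.4.4.6 lists eight events that may occur with PRO-231. Section 7.4.4.3 says burning, foreign body sensation and pruritus are not handled as AEs, and 7.4.2.1 removes hyperemia and chemosis. If that list were the expectedness reference, 8 − 3 − 2 = 3 would remain: dysgeusia, photophobia and corneal precipitates. This is conditional, because section 2.1 lists more reactions and the plan names no reference list.

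**Step 5: sensitivity of a secondary p-value.** The secondary analysis uses the safety population, planned at 19 per arm (section 10.1.2). With x events in one arm and 0 in the other, and equal arms of 19, the two-sided Fisher p is 2 × C(19, x) / C(38, x).

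- x = 5: 2 × 11,628 / 501,942 = 0.046.
- x = 4: 2 × 3,876 / 73,815 = 0.105.

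Counting or not counting one subject's event can therefore move the result across 0.05. The counts are hypothetical and do not forecast AE rates.

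**The case against.** The strongest reply is that Table 5 is the outlier. The synopsis, objectives, outcome section and Table 2 all require relatedness. Section 10.3 sends the analyst to Table 2 to categorise the variables, so one footnote should not be taken to govern. It is also fair to say that section 8.3 concerns reporting and not a test between arms, and that sections 8.5 and 8.5.3 provide for AEs in the final report. Unrelated AEs would not be lost from the record. All of this stands, but it does not remove the contradiction. The footnote is an explicit statement in the analysis section about this one variable, and no rule of precedence is given. Nor is a listing in a report a specified comparison by arm.

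The sizing in section 10.1.1 uses subjects with at least one AE, ocular or non-ocular, with no relatedness condition. The all-cause reading is therefore not foreign to the plan.

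A reader might infer more than the documents support:

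- *That unrelated AEs are compared nowhere.* The four signs and four symptoms in step 3 are compared without a causality condition, and they include the local effects most relevant to an eye drop.
- *That a single investigator's opinion decides causality.* Section 8.5.4 allows the sponsor's pharmacovigilance unit to categorise it as well.
- *That the person judging causality may know the allocation.* Sections 4.2 and 7.3 say that the principal investigator is blinded and will not know it. The differing primary packaging does not show that this fails.

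An all-cause comparison would not remove all judgement either. Under section 7.4.4.6, examination findings enter the eCRF as AEs only if the principal investigator considers them so.

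**Conclusion.** The point holds as a conflict between definitions of one secondary variable. The plan can be followed in two ways that give different AE counts. Under the version in 7.4.2.1, AEs judged unrelated, other than the signs and symptoms with their own variables, are not compared between arms as AE incidence.

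The effect on event counts cannot be computed, because the documents give no expected split between related and unrelated AEs. The illustration (0.046 against 0.105) assumes 19 dosed subjects per arm and all events in one arm.

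A reader might infer that the choice could reverse the trial's conclusion. It cannot: the synopsis and section 3.2 tie rejection of H0 to the primary variables, and this variable is secondary. The matter should be settled because safety is the main objective and the correction is cheap.

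**What to change.** Before unblinding, make the synopsis, section 3.1.2.2, section 7.4.2.1, Table 2 and Table 5 agree:

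1. Specify a by-arm comparison of subjects with any AE after first dose, regardless of causality, in the safety population.
2. Keep expected and intervention-related AEs, excluding hyperemia and chemosis, as a stated subset of that comparison.
3. Name the causality categories in section 8.5.4 that count as related.

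Reconciling the wording either way would end the contradiction. The all-cause comparison also closes the gap in step 2. AEs are already to be recorded whatever their cause (sections 7.4.4.6 and 8.5.1), so the cost is one extra table and no new data collection.
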